16.5.1 Subset Analysis by IgE

Anti-avelumab IgE will be assessed in a subset of samples covering ADA results and IgE positive and negative subjects from SAF analysis set. This analysis will only be performed for CSRs with integration across all dose expansion cohorts.

A listing of IgE result, ADA result, pre-dose avelumab concentration (mg/L), and IRR status will be prepared for each sample tested. Avelumab concentrations, IgE assessments, ADA results, and

IRR status will be matched by visit/ dosing date for each subject. IRR status is derived as positive or negative if subjects have at least one or no treatment emergent IRR started on the dosing date or the following day, respectively. IgE status is derived as negative if the non-missing value is < 0.1 , or positive if the value is ≥ 0.1 . A descriptive (count and percentage) summary table will be presented for IgE status by IRR status and ADA result, the denominator will be the number of samples with valid ADA and IgE results from subjects dosed at the corresponding visit.

Two scatterplots will be created to graphically display the data, one for IgE results vs. ADA titer, and one for IgE results vs. avelumab concentration ($\mu\text{g/mL}$). ADA results of negative or positive-TNR, IgE value or avelumab concentration below LLOQ will be set to 0 in the plot.

17 Safety Evaluation

The subsections in this section include specifications for summarizing safety endpoints that are common across clinical trials such as AEs, laboratory tests and vital signs.

All safety analyses will be performed using the SAF, unless otherwise specified.

All safety parameters will be summarized by cohort(s) and/or pooled across cohorts, depending upon the purpose of the reporting. Primary and final analyses for a cohort will include safety data summarized by that cohort unless integrated safety analysis is performed on the same data cut.

17.1 Adverse Events

The severity of AEs will be graded using the NCI-CTCAE, version 4.0 except where CTCAE grades are missing. No imputation of missing grades will be performed. AEs will be coded according to latest available version of MedDRA. AEs of special interest include IRRs and immune related adverse events (irAEs), which are detailed in Section 17.1.4 and 17.1.5, respectively.

- **Treatment Emergent Adverse Events:** TEAEs are those events with onset dates occurring during the on-treatment period for the first time, or if the worsening of an event is during the on-treatment period as defined in Section 11.
- **Related Adverse Events:** adverse events with relationship to study treatment (relationship with study treatment = related) reported by the investigator and those of unknown relationship (i.e. no answer to the question “Relationship with study treatment”).
- **Serious Adverse Events (SAE):** serious adverse events (as recorded on the AE eCRF page, serious adverse event = yes).
- **Adverse Events Leading to Treatment Discontinuation:** adverse events leading to permanent discontinuation of study treatment (as recorded on the AE eCRF page, action taken with study treatment = drug withdrawn).
- **Adverse Events Leading to Death:** adverse event leading to death (as recorded on the AE eCRF page, outcome = fatal or toxicity grade = 5).

- **Original Definition Immune Related Adverse Events (irAE):** irAEs are identified according to a pre-specified search list of MedDRA PTs, documented in a version-controlled repository maintained by the Sponsor and finalized for analysis prior to database lock. The original definition irAEs are utilized when the process for irAE medical review is either not followed or has not yet been completed for the delivery.
- **Updated Definition Immune Related Adverse Events:** irAEs according to case definition classified by medical review. Details are included in Table 15 in Appendix II.
- **Updated Definition Infusion Related Reaction:** IRRs are identified based on a list of MedDRA PTs. The detailed criteria of the timing relationship to infusion are specified in Table 16 in Appendix II.

AEs will be summarized using the MedDRA PT as event category and MedDRA primary SOC as summary category. All AE tables will be restricted to TEAEs unless otherwise specified.

Each subject will be counted only once within each PT or SOC and recording period. If a subject experiences more than one AE within a PT or SOC for the same recording period, only the AE with the strongest relationship or the worst severity, as appropriate, will be included in the summaries of relationship and severity. AEs with missing classifications regarding relationship to study treatment and start date greater or equal to start of study treatment will be considered as related to study treatment. AEs with missing toxicity grade will be counted into 'any grade' in the summarization by toxicity grade.

The AE tables will include the number and percentage of subjects with at least one TEAE, by MedDRA primary SOC (sorted by decreasing SOC frequencies within the overall column) and by PT (sorted by decreasing PT frequencies in overall column within SOC), unless otherwise stated.

17.1.1 All Adverse Events

All AEs will be tabulated in the following tables.

- The overall summary of AEs table will include the following summaries:
 - TEAEs
 - TEAEs, grade ≥ 3
 - Related TEAEs
 - Related TEAEs, grade ≥ 3
 - TEAEs leading to permanent treatment discontinuation
 - Related TEAEs leading to permanent treatment discontinuation
 - Serious TEAEs
 - Related serious TEAEs

- TEAEs leading to death
- Related TEAEs leading to death
- Treatment emergent irAEs
- Related treatment emergent irAEs
- Treatment emergent IRRs
- Related treatment emergent IRRs
- Incidence of TEAEs by SOC, PT, and worst grade
- Incidence of related TEAEs by SOC, PT, and worst grade
- Incidence of TEAEs by SOC and PT: displaying in separate columns the All TEAEs / Related TEAEs / Grade ≥ 3 TEAEs / Related Grade ≥ 3 TEAEs
- Incidence of TEAEs leading to death by SOC and PT
- Incidence of related TEAEs leading to death by SOC and PT
- Incidence of non-serious TEAEs by SOC and PT

Listing of AEs including all relevant information such as AE SOC/PT, start/stop date, duration of AE, toxicity grade, relationship to the study treatment, action taken with study treatment, and outcome etc., will be provided. A separate listing of AEs started or worsened after on-treatment period will also be provided.

17.1.2 Adverse Events Leading to Treatment Discontinuation

Following summary tables will be produced:

- Incidence of TEAEs leading to permanent treatment discontinuation by SOC and PT
- Incidence of related TEAEs leading to permanent treatment discontinuation by SOC and PT

The listing of AEs leading to permanent treatment discontinuation will also be provided with the relevant information such as AE SOC/PT, start/stop date, toxicity grade, and outcome etc.

17.1.3 Serious Adverse Events

Following summary tables will be produced:

- Incidence of serious TEAEs by SOC and PT
- Incidence of related serious TEAEs by SOC and PT

The listings of SAEs will also be provided with the relevant information such as AE SOC/PT, start/stop date, toxicity grade, relationship to the study treatment, action taken with study treatment, and outcome etc.

17.1.4 Infusion Related Reaction

IRRs will be summarized by the follow variables:

- Number of subjects with at least one event by the worst toxicity grade (grade 1/ grade 2/ grade 3/ grade 4/ grade 5/ missing grade)
- Number of subjects with IRR leading to permanent treatment discontinuation
- Time related to first onset (infusion 1/ infusion 2/ infusion 3/ infusion 4 or later). The events should be assigned to the actual drug infusions that the subject received, not to the planned dates. An IRR is assigned to a drug infusion if its onset is at the same date (but not before dosing) or the following day of drug infusion.
- Number of subjects with at least one event by the worst toxicity grade that occurred in the presence of premedication (grade 1/ grade 2/ grade 3/ grade 4/ grade 5/ missing grade). The denominator will be the number of subjects with at least one dose administered in the presence of pre-medication. The maximum toxicity will be derived among those IRRs that occurred in the presence of premedication.
- Number of subjects with at least one event by the worst toxicity grade that occurred in the absence of premedication (grade 1/ grade 2/ grade 3/ grade 4/ grade 5/ missing grade). The denominator will be the number of subjects with at least one dose administered in the absence of pre-medication. The maximum toxicity will be derived among those IRRs that occurred in the absence of premedication.

The listing of IRRs will be provided with the relevant information such as AE SOC/PT, start/stop date, toxicity grade, relationship to the study treatment, action taken with study treatment, outcome, premedication, and study medication batch ID etc.

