In total, 134 subjects (27.9%) treated during the dose expansion died up to the cut-off date (05 November 2014). Of these, the majority of deaths (101 deaths; 21.0%) were due to disease progression. An additional 8 deaths (1.7%) were due to TEAEs unrelated to trial treatment, 4 deaths (0.8%) were due to TEAEs related to trial treatment, and the reason for 8 deaths (1.7%) was labeled as other. The reason for 13 deaths (2.7%) was unknown at the time of the data cut-off. Of the 134 subjects who died, 53 subjects (11.0%) died within 30 days of the last administration of trial treatment. Among these deaths, 39 (8.1%) were due to disease progression, 7 (1.5%) were due to TEAEs unrelated to trial treatment, 4 (0.8%) were due to TEAEs related to trial treatment, and 3 (0.6%) were due to other reasons. No death of unknown reason was reported in the 30-day period.

Treatment-emergent AEs Leading to Permanent Discontinuation of Avelumab

A total of 80 subjects (16.7%) treated during the dose expansion withdrew permanently from trial treatment due to 1 or more TEAE. In 25 (6.6%) of these subjects, the TEAEs leading to treatment discontinuation were considered related to trial treatment by the investigator. These TEAEs were infusion-related reaction (6 withdrawals; 1.6%), GGT increased (3 withdrawals, 0.8%), dyspnea (3 withdrawals; 0.8%), and radiation pneumonitis, aspartate aminotransferase (AST) increased, hepatocellular injury, blood creatine phosphokinase increased, blood pressure increased, pneumonitis, anaphylactic reaction, food allergy, adrenal insufficiency, anemia, hypercalcemia, hyperglycemia, arthralgia, arthritis, myositis, pain, abdominal pain lower, chest discomfort, cramps and ache on back and all over body (not yet coded), encephalopathy, syncope, and flushing (1 withdrawal each; 0.3%).

Most of the events of infusion-related reaction and anaphylactic reaction that led to permanent discontinuation of trial treatment (as described above) occurred before implementation of mandatory premedication on 28 January 2014.

Immune-related Adverse Events

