17.1.4 Infusion Related Reactions

IRRs will be summarized by the follow variables:

- Number of subjects with at least one event by the worst toxicity grade (grade 1/ grade 2/ grade 3/ grade 4/ grade 5/ missing grade)
- Number of subjects with IRR leading to permanent treatment discontinuation
- Time related to first onset (infusion 1/ infusion 2/ infusion 3/ infusion 4 or later). The events should be assigned to the actual drug infusions that the subject received, not to the planned dates. An IRR is assigned to a drug infusion if its onset is at the same date (but not before dosing) or the following day of drug infusion.
- Number of subjects with at least one event by the worst toxicity grade that occurred in the presence of premedication (grade 1/ grade 2/ grade 3/ grade 4/ grade 5/ missing grade). The denominator will be the number of subjects with at least one dose administered in the presence of premedication. The maximum toxicity will be derived among those IRRs that occurred in the presence of premedication.
- Number of subjects with at least one event by the worst toxicity grade that occurred in the absence of premedication (grade 1/ grade 2/ grade 3/ grade 4/ grade 5/ missing grade). The denominator will be the number of subjects with at least one dose administered in the absence of premedication. The maximum toxicity will be derived among those IRRs that occurred in the absence of premedication.

The listing of IRRs will be provided with the relevant information such as AE SOC/PT, start/stop date, toxicity grade, relationship to the study treatment, action taken with study treatment, outcome, premedication, and study medication batch ID etc.

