Per protocol, avelumab will be administered as 1-hour i.v. infusion. Subjects will receive the study treatment once every 2 weeks. Dose delays will be grouped into the following categories based on the deviation of the actual to the planned treatment administration day (relative to the previous non-zero dose date): no delay (including 1-2 days delays), 3-6 days delay, 7 or more days delay. For example, if one subject receives the study treatment on day 1, then the next study treatment administration date will be on day 15; however, if the subject receives the study treatment at day 16 or 17, this is considered as 'no delay'. Any zero dose prior to the last treatment administration is considered as a dose interruption.

The summary of dose delays will be based on the SAF and include the following categories:

- No delay
- 3-6 days delay
- 7 or more days delay

The categorization is based on the maximum length of delay, i.e. the worst case of delay if subjects have multiple dose delays.

A listing of study treatment administration will include subject identifier, study day, # of days relative to prior treatment, infusion rate, most recent body weight prior to infusion, actual/planned dose, batch ID, dose reduction/dose delay or interruption, and other relevant information collected on the Cohort Treatment MSB0010718C Administration Details eCRF page. A subset of this listing will be created for subjects with at least one dose reduction.

A listing of treatment exposure and compliance will include subject identifier, assigned dose level, and above derived variables summarized in the tables.

In order to mitigate infusion-related reactions, a premedication regimen of 25 to 50 mg diphenhydramine and 650 mg acetaminophen (i.v. or oral equivalent) is mandatory 30 to 60 minutes prior to each dose of study treatment starting on January 29, 2014. The compliance to this requirement will be summarized as numbers of subjects with 0, 1, 2, 3, 4 doses among the first 4 treatment administrations that were administered without pre-medication. For example: if a subject discontinued after 3 doses, and 2 of them were administered with premedication, the number for that subject would be 1.

A listing of premedication will include subject identifier, reported medication term, the relative time to the start of infusion, date/time of premedication, and dose (unit). A listing containing subject identifier, visit, and unique study treatment batch ID will also be created.

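### Infusion-reaction rates with and without premedication pool all infusion numbers, so in dose escalation, early expansion cohorts and pooled tables they can differ with no premedication effect

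*SAP*

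**What the plan says.** In the expansion SAP, section 17.1.4, the row with premedication is defined by: "The denominator will be the number of subjects with at least one dose administered in the presence of pre-medication". The row without premedication mirrors it: "The denominator will be the number of subjects with at least one dose administered in the absence of pre-medication". Grade is the worst over all infusions of that status: "The maximum toxicity will be derived among those IRRs that occurred in the presence of premedication". The dose-escalation SAP, section 17.1.4, has the same rule: "The denominator will be the number of subjects with at least one dose administered in the presence of premedication". One subject can be in both rows.

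Infusion number appears only in a separate line of the same summary: "Time related to first onset (infusion 1/ infusion 2/ infusion 3/ infusion 4 or later". That line is not crossed with premedication and has no per-infusion denominator.

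Premedication was switched on by date. Protocol section 3.4 says it applied to all trial subjects, and reports that most of the reactions leading to permanent discontinuation "occurred before implementation of mandatory premedication on 28 January 2014". Section 15 of the expansion SAP describes the regimen as mandatory "minutes prior to each dose of study treatment starting on January 29, 2014", and the dose-escalation SAP gives the same date. The expansion SAP then adds: "The compliance to this requirement will be summarized as numbers of subjects with 0, 1, 2, 3, 4 doses". It counts unpremedicated doses among the first four administrations, with no date limit. The dose-escalation SAP describes its version of that count as use of premedication, not compliance.

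**The concern.** Being in a row depends on having had any dose of that status, at any infusion number and in any quantity. The calendar switch makes the two rows differ in both respects. A subject already on treatment in January 2014 contributes first infusions to the row without and later infusions to the row with. A later starter contributes infusion 1 to the row with, and enters the row without only if premedication was missed at some point.

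If reaction risk falls over the first infusions, the two rates differ because of infusion mix. If risk is constant, they still differ because the rows cover unequal numbers of infusions per subject. At stake is how a descriptive safety table is read. The expansion SAP (section 5) sends planned analyses to study reports, submissions or manuscripts, and section 8.2 pools all expansion cohorts for the interim report.

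The compliance summary has a different fault. Doses given before the requirement existed count as failures to comply with it.

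**Working it through.** **Did subjects straddle the switch?** The first subject was planned for Q1 2013 (protocol 5.1.6). At a cut-off of 17 July 2014, the first 90 treated NSCLC subjects had a median follow-up of 6 months, range 3 to 10 (protocol 3.5.4). Counting back 6 months gives a median start around mid-January 2014, so roughly half began before the mandate. The documents do not say how many of them were still on treatment at the switch.

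**What is missing.** The plan states no figure for these rows, so there is none to reproduce. The documents give no IRR rate by infusion number and no count of doses by premedication status. Protocol 3.4 reports treatment-related IRR in 9.8% of 480 expansion subjects, which serves only as a rough scale. All inputs below are assumptions.

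**Illustration, no premedication effect.** Risk is 8% at infusion 1, 3% at infusion 2 and 0.5% at each later one. Pre-mandate starters have four unpremedicated infusions, and those who continue have eight premedicated ones. Later starters have eight infusions. Risk per subject = 1 − product of (1 − risk per infusion):

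- four infusions from the first: 1 − 0.92 × 0.97 × 0.995² = 0.1165
- eight later infusions: 1 − 0.995⁸ = 0.0393
- eight infusions from the first: 1 − 0.92 × 0.97 × 0.995⁶ = 0.1340

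| Mix | Without | With | With/without |
|---|---|---|---|
| Escalation-like: 40 before, 25 continue, 13 later | 11.7% | (25 × 0.0393 + 13 × 0.1340)/38 = 7.2% | 0.62 |
| Expansion-like: 100 before, 60 continue, 500 later, no omissions | 11.7% | (60 × 0.0393 + 500 × 0.1340)/560 = 12.4% | 1.06 |
| Same, but 120 of 500 (24%) omit once, late | (100 × 0.1165 + 120 × 0.005)/220 = 5.6% | 12.4% | 2.2 |

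In the last line, removing the omitted dose from the row with changes 12.4% only to about 12.3%.

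**Other assumptions, still no effect.** Take eight infusions per subject, and 60 pre-mandate starters with one to four unpremedicated infusions. Add 0, 60, 120, 420 or 1580 later starters with no omissions. The with/without ratios are:

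- steeply falling risk (6.5, 2.0, 0.8, 0.4%, then 0.05%): 0.17, 0.66, 0.82, 1.03, 1.12
- moderately falling risk (4.0, 2.5, 1.5, 1.0%, then 0.2%): 0.43, 0.92, 1.08, 1.28, 1.37
- flat 1% at every infusion: 2.2 rising to 3.1

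**A true halving of risk.** With 60 pre-mandate and 420 later starters and no omissions, the ratio is 0.52 (steep) or 0.65 (moderate). If later starters miss premedication at 5% of infusions 5 to 8, it becomes 1.19 or 1.43.

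**Splitting by infusion number.** At infusion 1 the modelled ratio is 1.00 when the true ratio is 1, and 0.50 when it is 0.5, in every mix with both statuses at infusion 1. Where all subjects started before the switch there is no premedicated infusion 1, and the empty cell would show that no comparison is possible.

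Withdrawal after a reaction on an unpremedicated dose is not modelled.

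**The case against.** The SAPs plan two descriptive rows, with no difference, ratio or test. Protocol 8.5.1 makes everything outside the primary endpoint of the efficacy expansion cohorts exploratory. That stands, and it limits the point to the reading of a table.

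A reader might infer that the table is the evidence on which mandatory premedication rests. The documents do not support that. Protocol 3.4 says the mandate followed two suspected unexpected serious reactions and a cumulative review, and no passage makes keeping premedication depend on these rows.

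A reader might also take the 5.6% against 12.4% line as an expected spurious doubling. It is not. It needs 24% of later starters to omit a mandatory premedication, each at a late infusion, and no document gives an omission rate. Without omissions the same mix gives 11.7% against 12.4%.

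Nor does straddling reach every cohort. By the safety cut-off of 5 November 2014, protocol 3.4 counts only 5 melanoma, 1 mesothelioma, 1 adrenocortical and 3 urothelial subjects. The urothelial efficacy cohort came with Amendment 10 in March 2015.

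Early clustering of reactions is an assumption too: the onset categories show only where onset is tabulated. The flat-risk case shows that the distortion does not need it.

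Finally, the listings would let a reader rebuild infusion-level status. That is true, but the summary rows would still carry the distortion.

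**Conclusion.** The point holds as a defect in a descriptive safety table. Followed exactly, section 17.1.4 of both SAPs yields two rates that can differ with no premedication effect, because the rows differ in infusion mix and in infusions per subject. It concerns dose escalation, the early expansion cohorts and tables pooled across cohorts. No primary or confirmatory result is affected.

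The direction is not fixed. A spurious benefit appears when most subjects straddle the switch and risk falls over the first infusions. The apparent effect shrinks or reverses as later starters dominate or premedication is missed late. The size cannot be fixed from the documents, since it rests on assumed risks, group sizes and omissions.

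The compliance point is separate and applies to the expansion SAP only. A reader might extend it to dose escalation, but that SAP reports use and claims no compliance.

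**What to change.** In both SAPs, section 17.1.4:

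- Cross the two rows with the existing infusion categories (1, 2, 3, 4 or later). Use as denominator the subjects who received that infusion under each status. The last category still pools several infusions, so give the number of infusions there as well.
- Show infusion 1 separately, by worst grade and premedication status.
- Footnote that the contrast is non-randomised and largely before against after the mandate. Splitting by infusion number does not remove differences in calendar time or tumor cohort.

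In the expansion SAP only, section 15: limit the premedication compliance summary to infusions on or after the mandate date. Before programming this, reconcile the date, which is 28 January 2014 in the protocol and 29 January 2014 in the SAPs.

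The cost is SAP wording, a re-specified IRR table in each SAP and a date restriction in one compliance table. The data are already collected: section 17.1.4 assigns reactions to actual infusions, and section 15 of the expansion SAP lists premedication date and time.
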